2 STATISTICAL AND ANALYTICAL PROCEDURE

Data collected in this study will be presented using summary tables, figures, and by-patient data listings. Descriptive statistics for categorical variables will be provided using frequencies (n) and percentages (%). Descriptive statistics for continuous variables will be provided using number of observations (n), mean, standard deviation (SD), median, minimum, and maximum.

If appropriate, p-values and 95% confidence intervals (CI) from analysis of covariance with baseline as covariate may be provided for change from baseline values. All data used in tabular summaries or figures will be supported by listings of underlying data – raw and/or derived, and all figures will be supported by relevant summary information.

2.1 SUBJECT DESCRIPTION

2.1.1 Disposition of subjects

Screened patients are defined as any patients who signed the informed consent or whose parent or guardian signed informed consent.

Enrolled patients are defined as those who meet the inclusion criteria and none of the exclusion criteria.

The number of patients screened, enrolled, treated (receiving at least one study infusion), completing the study, and not completing study along with primary reason for discontinuation will be presented.

2.1.2 Protocol deviations

During the review of the database, compliance with the protocol will be examined with regard to inclusion and exclusion criteria, treatment, prohibited therapies, and timing and availability of planned assessments. Protocol deviations will be identified by the study team before database lock and classified as minor, major or critical deviations. A listing of major or critical protocol deviations for all treated patients will be produced.

In addition to the above, the two conditions listed below will be evaluated:

- Noncompliance: Missing 2 or more consecutive infusions (excluding for cause missed doses, such as when the missed infusions are required by the protocol due to a dose limiting toxicity) or a total of 4 or more infusions for the 64-week treatment period. Whether a missed infusion is for-cause or not will be reviewed and determined by the clinical team; the decision will be used in the determination of noncompliance.
- Prohibited medications intake: A list of medications which potentially modify the effect of olipudase alfa are identified and provided by the clinical team. This list is updated regularly with change of World Health Organization (WHO) Drug dictionary (WHO-DRUG) versions. Any use of such medications in the clinical database will be reviewed by

the clinical team before data base lock with special attention to start and/or stop date of these medications compared to start/stop date of study treatment. The clinical team will review the prohibited medication intake and decide whether it is minor, major or critical protocol deviation.

2.2 ANALYSIS POPULATIONS

2.2.1 Safety population

All subjects who were exposed to the study treatment, olipudase alfa, ie, who received at least one infusion of study treatment (total or partial), will be included in the safety population.

2.2.2 Modified intent-to-treat population

The modified intent-to-treat (mITT) population is the same as the safety population and is used as the primary population for the efficacy analysis.

2.2.3 Pharmacokinetic population

The pharmacokinetic population includes all patients who receive at least 1 infusion of olipudase alfa and have evaluable pharmacokinetic data available post-baseline.

2.2.4 Pharmacodynamic population

Pharmacodynamic population includes all patients who are treated and have at least one evaluable pharmacodynamics measurement available post-baseline.

2.3 DEMOGRAPHIC AND BASELINE CHARACTERISTICS

2.3.1 Subject demographic characteristics, medical history, and diagnoses

Demographic, disease characteristics and medical/surgical history information will be summarized by age group cohorts and overall using the safety population. No formal hypothesis testing will be performed to compare differences between age group cohorts.

Demographic and baseline characteristic parameters include the following: gender, race, ethnicity, ancestry, age (in years and months) at Week 0/Day 1, human immunodeficiency virus (HIV) antibody testing, and Hepatitis tests (B surface antigen and C antibody tests).

Baseline disease characteristic parameters include the following: age at ASMD symptom onset (years and months if available), age at ASMD diagnosis (years and months if available), spleen status, ASMD symptoms present at disease onset, ASMD family history, genotyping of acid sphingomyelinase gene (SMPD1), CHIT1, UGT1A1, severe splenomegaly and severe % predicted DLco adjusted for hemoglobin. Genotype of acid sphingomyelinase gene (SMPD1), CHIT1 and UGT1A1 as well as acid sphingomyelinase (ASM) activity in peripheral leukocytes and CRIM

testing from screening evaluations will be included in data listings. Severe splenomegaly is defined as the baseline spleen volume (MN) > 15 MN; severe % predicted DLco adjusted for hemoglobin is defined as the baseline value < 40%.

The SMPD1 variant type (i.e., missense, frameshift, deletion, nonsense, etc.) will be derived, if possible, from the SMPD1 amino-acid change.

For the classification of CHIT1 genotype, the following derivation will be applied:

- N= Wildtype (WT)/WT = Normal / 2 functional alleles
- H= WT/Duplication 24 (DUP24) = Heterozygous mutation /1 functional allele
- M = DUP24/DUP24 = homozygous mutation / 2 non-functional alleles (no chito activity)

For the classification of UGT1A1 genotype, the following derivation will be applied:

- UGT1A1*1 = Fully functional allele = Not Gilbert variant
- UGT1A1*36 = Functional allele = Not Gilbert variant
- UGT1A1*28 = Gilbert syndrome allele = Gilbert variant
- UGT1A1*37 = Crigler-Najjar syndrome type 2 allele (impaired UGT1A1) = Gilbert variant

Patients with 0 or 1 Gilbert variant alleles will be classified as “no Gilbert Syndrome”; patients with 2 Gilbert variants alleles will be classified as “Gilbert Syndrome”.

Medical/surgical history will be collected by body system as Yes/No/Unknown, and if Yes, the current status will be collected. These data will be summarized by body system, by age group cohorts and overall. Additional medical/surgical history regarding specific disease of interest will be collected and summarized.

Smoking and alcohol drinking history data will be provided in data listings.

2.3.2 Baseline safety parameters

Baseline for safety parameters (weight, height, body mass index (BMI), physical exam, vital signs, echocardiograms, immune response assessments, and safety biomarkers) in general is defined as the last available non-missing value for the parameter before the first infusion. Most of the baseline values will thus be Day 1/Week 0 pre-infusion assessments with the exception of hematology parameters and possibly electrocardiogram (ECG). Hematology samples are collected twice at screening and twice on first infusion visit, once before and once after the first infusion; the average of all measurements taken before the first infusion will serve as the baseline. Another exception may be the ECG parameters – Day 1/Week 0 (the first infusion visit) is to collect ECG in triplicate before the infusion; if 2 or more than 2 of these triplicate collections of ECG are before the first infusion, the average of these ECG parameter results will be considered as the baseline value; otherwise, the baseline value of ECG parameters will be taken from the latest observation before the first infusion.

Baseline safety data will be presented along with subsequent values assessed during or after olipudase alfa dosing using safety population.

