Clinical chemistry g , hematology g , coagulation g , urinalysis g	X	X		X		X				X	X	X											
$\beta$ -hCG pregnancy test i	X	X	Every 4 weeks from Day 1: Wk4, Wk8, Wk12, Wk16, Wk20, Wk24, Wk28, Wk32, Wk36, Wk40, Wk44, Wk48, Wk 52, Wk 56, Wk 60, Wk 64								X												
Safety biomarkers g		X	X	X	X	X	X			X	X	X	X										
Anti-olipudase alfa IgG and neutralizing antibodies in IgG positive patients		X	Every 2 weeks from Day 1 through Wk16, then at quarterly visits (Wk26, Wk38, Wk52) and Wk 64										X										
Anti-olipudase alfa IgE antibody test		In the event of a moderate/severe or recurrent-infusion associated reaction suggestive of hypersensitivity, a sample will be collected $\geq$ 3 days after event or prior to next infusion.																					
Serum tryptase and complement activation		In the event of a moderate/severe or recurrent-infusion associated reaction suggestive of hypersensitivity, a sample will be collected within 1 to 3 hours of event onset.																					
Skin testing		As necessary for assessing hypersensitivity reactions. See study manual.																					
Exploratory efficacy																							
Spleen volume by abdominal	X						X				X		X e										

DAY/WEEK (Wk)	Screening		Treatment Period a, b									Post-treatment Observations	
	Day -60 to Day -1	Day1 /Wk0	Wk 2 to Wk 10	W12 QV	Wk 14 to Wk 24	Wk 26 QV	Wk 28 to Wk 36 c	Wk 40 to Wk 50, Wk 54 to WK 62	Wk 38 QV	Wk 52 QV	Wk 64	Withdrawal	Follow-up
MRIj													
Liver volume by abdominal MRI j	X						X			X		X e	
Pulmonary imaging with HRCT	X									X		X e	
Pulmonary function test k	X						X			X		X e	
Chest X-ray l	X									X		X e	
Bone age by hand X-ray	X									X		X e	
Cycle ergometry m	X						X			X		X e	
Physician's global assessment	X						X			X		X	
Efficacy biomarkers		X					X			X	X	X	
Lipid profile	X	X n		X n			X			X	X	X	
Serum bone-specific ALP and C-telopeptide n		X					X			X	X	X	
Health outcome questionnaires	X						X			X		X e	
Cognitive and adaptive function testing o	X						X			X		X e	
Pharmacodynamics													
Plasma and/or DBS sphingomyelin and metabolite concentrations g			X	X	X	X	X			X	X	X	X

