	Dose escalation visits & 2 nd infusion at highest tolerated dose				Quarterly visits (day 1/wk0, wk12, wk26, wk38, wk52)				Week 64
	Pre-infusion	End of infusion	24 hr	48 hr	Pre-infusion	End of infusion	24 hr	48 hr	
Electrocardiogram	X a	X a	X a	X a	X b	X	X c	X	
Liver function testing	X		X c	X	X		X c	X	X
Clinical chemistry & coagulation					X		X c	X	X
Urinalysis					X				X
Hematology					X d		X c	X	
Safety biomarkers:									
Ceramide	X		X c	X	X		X c	X	X
Cardiac troponin-1	X		X c	X	X		X c	X	X
hsCRP	X		X c	X	X		X c	X	X
Calcitonin	X		X c	X	X		X c	X	X
Iron and ferritin	X		X c	X	X		X c	X	X
IL6 and IL8 e	X		X c	X	X f		X c,f	X f	
Plasma and/or DBS sphingomyelin and metabolite concentrations g	X		X c	X	X		X c	X	X

Note: When multiple assessments are required, the order should be vital signs before ECG before PK or blood draws. Preinfusion assessments are to be completed within 24 hours prior to olipudase alfa infusion. End of infusion assessments are to be completed with 10 minutes following the end of olipudase alfa infusion. Twenty four (24) hour and 48 hour post infusion assessments to be completed within  $\pm$  3 hours of scheduled time.

a At each new dose of  $\geq 0.3$  mg/kg only.

b ECG in triplicate on day 1/week 0

c Sample/assessment is not required in patients in the child cohort (patients aged 6 to <12 years) or in patients aged 3 to < 6 years.

d Two samples to be collected within 24 hours of olipudase alfa at week 52. See [Section 10.3.5](#) for details.

e Sample not required in patients aged 3 to < 6 years.

f Sample not required at week 26, week 38 or week 52.

g DBS collection not required in patients aged 3 to < 6 years.

Abbreviations: hr = hour; hsCRP = high sensitivity C reactive protein; IL = interleukin; wk = week.

**1.4 SUPPLEMENTAL FLOWCHART - DAY 1/WEEK 0, DOSE ESCALATION VISITS, SECOND INFUSION AT THE HIGHEST TOLERATED DOSE, QUARTERLY VISIT AND WEEK 64 ASSESSMENTS IN PATIENTS ≤ 2 YEARS OLD**

	Day 1/Week 0			Dose escalation visits & 2 nd infusion at highest tolerated dose			Quarterly visits (wk12, wk26, wk38, wk52)			Week 64

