	Pre-infusion	End of infusion	48 hr	Pre-infusion	End of infusion	48 hr	Pre-infusion	End of infusion	48 hr	
Electrocardiogram	X a			X b	X b	X b	X	X	X	
Liver function testing			X	X		X	X		X	X
Clinical chemistry & coagulation			X				X c		X c	X
Urinalysis	X						X			X
Hematology			X				X d		X	
Safety biomarkers:										
Ceramide	X		X	X		X	X		X	X
hsCRP			X	X		X	X		X	X
Calcitonin	X		X	X		X	X		X	X
Ferritin	X		X	X		X	X		X	X
Plasma sphingomyelin and/or metabolite concentrations	X		X	X		X	X		X	X

Note: When multiple assessments are required, the order should be vital signs before ECG before PK or blood draws. Preinfusion assessments are to be completed within 24 hours prior to olipudase alfa infusion. End of infusion assessments are to be completed with 10 minutes following the end of olipudase alfa infusion. Twenty four (24) hour and 48 hour post infusion assessments to be completed within  $\pm$  3 hours of scheduled time.

*a* In triplicate

*b* At each new dose of  $\geq 0.3$  mg/kg only.

*c* Assessment not required at week 12 quarterly visit.

*d* Two samples to be collected within 24 hours of olipudase alfa at week 52. See [Section 10.3.5](#) for details.

Abbreviations: wk, week; hr, hour; hsCRP, high sensitivity C reactive protein.

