#### **6.4.1 Specific parameters rationale**

##### **6.4.1.1 Safety**

Data collected in the phase 1 single ascending dose study with olipudase alfa in ASMD adult patients demonstrated dose-related increases in ceramide, bilirubin, hsCRP, and other acute phase reactants that peaked 24 to 48 hours post-dose and resolved by Day 14 (5). With the use of a progressive dose escalation regimen in the Phase 1b adult ASMD, such increases in ceramide, bilirubin, hsCPR and other acute phase reactants were attenuated, with the majority of AEs being mild (6).

As a result, safety biomarkers for the monitoring of olipudase alfa in pediatric patients include, but are not limited to, hsCRP, ceramide, iron, ferritin, cardiac-specific troponin I, calcitonin, interleukin (IL)-6 and IL-8.

An immune reaction against an exogenously administered recombinant protein plays a critical role in the safety of such compounds. Therefore, safety assessments will also include blood samples for anti-olipudase alfa immunoglobulin G (IgG) antibodies and neutralizing antibody formation in patients testing positive for IgG.

In the event that a patient experiences a moderate, severe, or recurrent IAR suggestive of hypersensitivity reactions, additional blood samples will be collected for the evaluation of:

- circulating immune complex detection; and
- immunoglobulin E (IgE), serum tryptase, and complement activation.

Additionally, skin testing may be performed, as appropriate, in patients who experience an IAR that meets the following criteria:

- Infusion associated reaction is suggestive of IgE-mediated hypersensitivity reaction, with persistent symptoms of bronchospasm, hypotension and/or urticaria requiring intervention;
- or any other signs or symptoms at the discretion of the investigator or the sponsor.

Skin testing may be another predictor of IgE-mediated reaction and may be suggested for confirmation of the IgE results.

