1.3 DETERMINATION OF SAMPLE SIZE

A sample size power calculation was not performed for this study. The study sample size is based upon empirical considerations.

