2.6.10 Safety biomarkers

Biomarkers for monitoring the safety of olipudase alfa include, but are not limited to, high sensitivity C reactive protein (hsCRP), plasma ceramide, iron, ferritin, cardiac-specific troponin-1, calcitonin, interleukin (IL)-6 and IL-8. Samples will be collected at the visits specified in Protocol Sections 1.2 and 1.3.

Observed values, change from baseline and percent change from baseline will be summarized by age group cohorts and overall at each time point. Summary plots over time will also be presented for observed values as appropriate.

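### Flowchart 1.4 schedules no hsCRP sample before the first infusion in patients aged 2 years or under, so their planned change from baseline cannot be derived unless an unscheduled value exists

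*SAP*

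**What the plan says.** **Analysis.** Safety biomarkers, hsCRP among them, belong to the primary safety endpoint (Protocol 9.1, 9.1.9). Protocol 11.4.2.7 names hsCRP for change-from-baseline summaries by age cohort. SAP 2.6.10 adds percent change: "change from baseline and percent change from baseline will be summarized by age group cohorts" and overall, at each time point.

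**Baseline.** Under SAP 2.3.2 the baseline for these parameters "in general is defined as the last available non-missing value for the parameter before the first infusion". That section expects most baselines to be Day 1 pre-infusion values and names only hematology and possibly ECG as exceptions. SAP 2.11.2 plans no imputation in general.

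**Sampling.** Protocol 10.3.2 sends sites to flowcharts 1.3 and 1.4 for the Day 1 biomarkers. Flowchart 1.3 covers patients aged 3 and over and has a pre-infusion hsCRP sample. Flowchart 1.4 covers patients aged 2 or under. There the Day 1 pre-infusion cell for hsCRP is empty and the 48-hour cell is marked, while ceramide, calcitonin and ferritin are marked at both.

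**The concern.** A change-from-baseline table needs a pre-treatment value, and for this marker in this age group the plan schedules none. Liver function, chemistry/coagulation and hematology also have no Day 1 pre-infusion sample in flowchart 1.4, but each has a screening sample to fall back on. hsCRP does not.

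The marker is not incidental. Protocol 6.4.1.1 reports from the adult single-dose study "increases in ceramide, bilirubin, hsCRP, and other acute phase reactants that peaked 24 to 48 hours post-dose", and Protocol 10.6.1.3.2.2 ties raised hsCRP to the acute phase reaction, which is an adverse event of special interest. SAP 1.5 explains that acute phase reactions cannot be listed separately, because only infusion-associated reactions were identified in the e-CRF, and moves them to narratives. That gives the biomarker summaries more weight as a systematic view of the reaction. As scheduled, the youngest patients would be absent from the change part of those summaries.

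**Working it through.** **Step 1. Is any hsCRP value scheduled before infusion 1 at age 2 or under?**

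| Place | What it provides |
|---|---|
| Protocol 1.2, screening | Safety biomarkers blank |
| Protocol 1.2, Day 1 | Safety biomarkers marked, but not split by analyte or by pre-/post-infusion |
| Protocol 1.4, Day 1 pre-infusion | hsCRP blank; ceramide, calcitonin, ferritin marked |
| Protocol 1.4, Day 1 48 h | hsCRP marked (after treatment) |
| Protocol 9.1.8, clinical chemistry | hsCRP not in the panel |
| Protocol Table 6, screening column | No safety-biomarker sample |
| Protocol 10.3.2 | Refers back to 1.3/1.4; adds no draw |

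Scheduled pre-treatment hsCRP values: 0.

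**Step 2. Are the blank Day 1 cells real?** Table 6 gives sample counts for this age group. I counted visits from flowchart 1.4 and Protocol 10.3.2 to 10.3.8, assuming no repeated or missed dose:

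- Day 1: pre-infusion (if marked) and 48 h
- 8 escalation or second-top-dose visits (Weeks 2, 4, 6, 8, 10, 14, 16, 18), 2 samples each: 16
- 4 quarterly visits (Weeks 12, 26, 38, 52), 2 each: 8
- 3 non-escalation visits before Week 26 (Weeks 20, 22, 24), 1 each: 3
- Week 64: 1

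With a Day 1 pre-infusion sample: 2 + 16 + 8 + 3 + 1 = 30. Without it: 1 + 16 + 8 + 3 + 1 = 29.

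Table 6 states 30 for safety biomarkers (30 × 4.4 mL = 132 mL) and 29 for liver function (29 × 1.1 mL = 31.9 mL). Both reproduce. Table 5, for older children whose flowchart marks both at Day 1 pre-infusion, states 30 for each. Chemistry (1 + 2×3 + 1 = 8, Week 12 not required) and hematology (1 + 2×4 + 1 extra Week 52 sample = 10) also reproduce with the blank cell.

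This is support, not proof. The same count gives 8 for coagulation and 30 for sphingomyelin, against 11 and 29 in Table 6. Table 6 also counts biomarkers as one set, so its 30 cannot show whether hsCRP is part of the Day 1 pre-infusion draw. The hsCRP row of flowchart 1.4 decides that, and there the cell is blank.

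**Step 3. Effect on the planned analysis.** Change = value − baseline; percent change = 100 × (value − baseline) / baseline.

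- As scheduled: 29 hsCRP values, 0 before infusion 1, so 0 of 29 changes can be derived.
- With one Day 1 pre-infusion value: 30 values and 29 of 29 changes.

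**Step 4. What survives.** All observed values, plus a same-visit pre-infusion/48-hour pair at each of 8 + 4 = 12 later escalation and quarterly visits.

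**Step 5. How many patients.** The only minimum is 2 + 2 = 4 from birth to under 6 years (Protocol 11.1); none is set for age 2 or under. Purely as illustration, with the cohort at that minimum of 4 and the study at its minimum of 20:

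| Aged ≤2 (assumed) | Cohort without hsCRP change | Overall |
|---|---|---|
| 0 | 0 of 4 | 0 of 20 |
| 1 | 1 of 4 (25%) | 1 of 20 (5%) |
| 2 | 2 of 4 (50%) | 2 of 20 (10%) |

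**The case against.** A reader might infer more than the documents support, and the other side has good answers to most of it.

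- **That no pre-treatment hsCRP will ever exist.** SAP 2.11.4 lets unscheduled values serve as baseline, and Protocol 9.5 allows extra samples at the investigator's discretion. The documents support only that none is scheduled.
- **That these patients vanish unnoticed.** SAP Section 2 reports n with every continuous summary and backs the tables with listings. The shortfall would be visible, though its cause would not.
- **That the first value sits on an acute-phase peak and cannot be interpreted.** The 24 to 48 hour peak comes from adults and was dose-related. The first pediatric dose is 0.03 mg/kg, one third of the 0.1 mg/kg that Protocol 6.4 reports as free of related adverse events in that study. A material rise at this dose is not shown. The adult rises had also resolved by Day 14, so the Week 2 pre-infusion value is a plausible reference. It still follows the first infusion, so it cannot be the baseline under SAP 2.3.2.
- **That acute phase reactions go unassessed.** They are judged on combined laboratory and clinical findings. Ferritin has a Day 1 pre-infusion value, and neutrophils, albumin and clotting times have screening values.
- **That the fix is certainly free.** At Day 1 pre-infusion, hsCRP follows the pattern of the liver, chemistry and hematology rows, so it may share a tube that is not drawn then, perhaps to spare blood in the smallest children. The documents give no tube assignments and do not say whether the blank is a slip or a choice.

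The affected group may also be empty: Protocol 4.1 says type B disease is typically diagnosed after age 2. All of this limits the size of the problem. None of it supplies the missing scheduled value.

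**Conclusion.** The point holds for one marker in one age group. Followed as written, the plan asks for a change and percent change in hsCRP that cannot be computed for any patient aged 2 or under who lacks an unscheduled pre-infusion value: 0 of 29 scheduled values. Such patients contribute nothing to the hsCRP change summaries for the infant/early child cohort or overall. Their observed values and 12 same-visit pairs remain usable, and the other biomarkers in flowchart 1.4 are unaffected.

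The number of patients concerned is unknown and may be zero. The 25% and 50% figures above depend on an assumed one or two such patients in a cohort at its minimum size and are not an estimate. The count of 29 assumes no repeated or missed dose; the zero does not depend on it. The reading rests on the hsCRP row of flowchart 1.4. The footnote to the safety-biomarker row in flowchart 1.2 could not be read in the text available.

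This is a gap between schedule and analysis within the primary safety endpoint. It is worth closing because closing it is easy, but it does not undermine the safety evaluation as a whole.

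**What to change.** 1. **Protocol 1.4:** mark hsCRP at Day 1/Week 0 pre-infusion, run on the safety-biomarker draw already scheduled then for ceramide, calcitonin and ferritin. Table 6 counts 30 draws of 4.4 mL, which by the count above includes that one, so no extra blood is needed if the tube can carry hsCRP. The laboratory should confirm this. If it cannot, allow a small extra volume (assumed about 1 mL; the documents give no figure), which must fit the cap of 7 mL/kg in any 8 weeks in Protocol 9.5.
2. **Patients already dosed without such a value:** test stored pre-infusion samples where consent and stability allow.
3. **Where that is not possible, SAP 2.6.10:** state that hsCRP change from baseline is not estimable at age 2 or under. Report observed values and the change from the same-visit pre-infusion value, each with the contributing n.
4. **Cross-references:** add Section 1.4 to the sampling references in Protocol 9.1.9 and SAP 2.6.10. Both cite only Sections 1.2 and 1.3, and 1.3 does not cover these patients.

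The cost is one flowchart cell, two cross-references, a laboratory query and, if needed, a short SAP paragraph.
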